
Preconditions

The focus is on providing treatment to the entire family to overcome parenting challenges. Frontline practitioners and senior managers trained in the MST-CAN model. Ongoing regular supervision. Access to clinical input from therapists and psychiatris to play a role in delivering the intervention and supporting and supervising staff within the services. Staff are skilled in completing functional assessments, safety planning, and family needs assessment. Provision of services according to need, including parenting training, psychotherapy, anger management, family therapy and substance use treatment.

Research questions.

Research questions for the pilot trial are.

- **RQ1** To report on a two-armed cluster randomised pilot trial across three geographical areas in England and Wales.
- **RQ2** To measure pre-defined progression criteria to assess the feasibility for a definitive randomised controlled trial to evaluate efficacy
- **RQ3** To report on strategies to maximise recruitment and retention and how they should be implemented in a definitive study
- **RQ4** To report on the correlation between the primary outcome collected by parents and school to provide an indication of the most efficient method of collecting the primary outcome in a definitive trial for children aged less than 11 years.
- **RQ5** To report on the feasibility of collecting children's social care outcome data; rereferrals for child abuse and neglect, transitions from child protection to child in need, transitions from child protection to public law outline and/ or looked after child, child placed outside the family home, time on child protection register and recommend appropriate children's social care outcomes for a definitive trial
- **RQ6** To estimate the mean family size and the family intra-class correlation coefficient (ICC) to inform a sample size calculation for a definitive efficacy study.
- **RQ7** To estimate the pre- post-test correlation of the primary outcome measure to inform a sample size calculation for a definitive trial.
- **RQ8** To assess the quality of data completion at each assessment point to provide an indication of outcome measure redundancy.
- **RQ9** To provide an initial estimate of potential effect of MST-CAN versus BAU within 80% confidence intervals.
- **RQ10** To quantitively assess compliance with planned interventions in MST-CAN.

RQ11 To quantitively assess MST-CAN fidelity.

Success criteria and/or targets

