- 3. Usually resident in the local authority.
- 4. One parent and at least one child willing and able to provide informed consent. Consent will be taken from parents for themselves, and any child aged less than 16 years, children aged 16 years or more will provide their own consent.

Exclusion criteria

1. A child who has already been placed away from home with no prospect of reconciliation.

- 2. A child living independently.
- 3. Current actual or suspected sexual abuse involving family members.
- 4. Primary referral reason is a child's serious mental health issue.
- 5. Referred child assessed as being actively suicidal or homicidal.

Potentially eligible family referred for MST-CAN Family assessed for suitability by MST-CAN team, If ineligible family receive BAU study explained and provided with information sheet If no consent family receive Consent forms signed and BAU referred to evaluation team Evaluation team make contact and conduct baseline assessment Randomised to MST-CAN or BAU Evaluation team inform MST-CAN team and family of the allocation Evaluation team makes contact at 3 months Evaluation team makes contact at 6 months Evaluation team makes contact at 9 months and conducts follow-up assessment

Participant flow through the trial

Sample size

In the pilot study we will recruit 72 participants, 36 in each arm, across the 3 sites, with the expectation that we will successfully follow-up 58 at month 9. This will allow for exploration of key parameters needed to confirm sample size calculation for the efficacy study. It is

sufficient to allow estimation of two-sided 95% CIs around the proportions of eligible, consenting, adhering and followed-up at month 9 in each arm of the study with half-widths less than 0.15. It exceeds the 30 per group recommended by Lancaster et al (Lancaster et al., 2004) and the 35 per group recommended by Teare et al (Teare et al., 2014) for estimating the SE of a primary outcome with sufficient precision, including accounting for any variation across site, where 12 participants per arm per site is recommended.

Outcome measures

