Wellbeing will be assessed using the short form, 10-item, KIDSCREEN10 (Ravens-Sieberer et al., 2014), this valid-reliable instrument suitable for completion by children aged 7 years or more demonstrates excellent reliability and validity in the target population (Cronbach's α 0.82).

Psychological health will be assessed using the Revised Child Anxiety and Depression Scale (RCADS-25; (Ebesutani et al., 2017, Ebesutani et al., 2012). This 25-item scale assesses both depression and anxiety and both the child and parent completed version have established reliability and validity. Trauma related psychological health will be assessed using the 8-item Child Revised Impact of Events Scale (CRIES-8; (Perrin et al., 2005). This validated instrument is widely used as a screening tool to identify Post Traumatic Stress Disorder in children and adolescents.

For children in school we will assess school belonging using the School Connectedness Scale (SCS; (Brown et al., 2000)). This 16-item scale assesses school connectedness across three domains: belief, belonging and commitment. The scale has established validity and reliability (Cronbach's α 0.86) and higher school connectedness is associated with greater school attendance and better school outcomes.

We will use six questions derived from a Client Service Receipt Inventory (CSRI; (Coulton et al., 2022)) to assess the frequency of school attendance, exclusions and suspensions, and criminal justice involvement over the previous 9-months. Client Service Receipt Inventory methods are an established and valid form of assessing participant resource use in randomised controlled trials and can be adapted for the target population (Knapp and Beecham, 1990).

Parent-related outcomes

We will collect indicators of future child abuse and neglect following baseline measures including any further referrals, children's social care interventions or out of home placements over the nine months from baseline to follow-up.

We will include a measure of family environment that assesses relationships, conflict, and cohesion via the Brief Family relationship Scale (BFRS; (Fok et al., 2014)). We will assess the potential for child abuse and neglect using the Parent-Child Conflict Tactics Scale (CTSPC; (Straus et al., 1998). This 22-item questionnaire assesses the frequency of parent to child conflict and includes items on non-violent discipline, psychological aggression, physical assault and neglect.

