RQ2 - We will estimate likely proportions of participants who are eligible, who consent, the proportion followed-up at 9-months, the proportion who adhere and the data completeness of primary, secondary outcomes and process outcomes. Each of these will be assessed against progression criteria agreed a priori

RQ3 – We will leverage the qualitative work planned under IPE Q2, specifically targeting retention and barriers. By conducting semi-structured interviews with 5-10 parents who initiated but did not continue the intervention, we aim to identify the underlying reasons for dropout and gather insights that could inform improvements in retention strategies. Additionally, interviews with another 5-10 parents who declined to participate will help us understand barriers to entry into the study. The data collected from these interviews will help refine recruitment techniques to enhance engagement and consent rates. We will report on strategies identified to maximise recruitment and retention from our qualitative work and where appropriate include them in the pilot study.

RQ4 - We will conduct a correlation analysis to explore the relationship between parent and school completed SDQ. First exploring the distribution of the outcome at each time-point and then selecting the appropriate parametric or non-parametric correlation approach. This will inform a decision regarding the relative utility of each approach and the source of the primary outcome for a definitive trial.

RQ5 - We will integrate questions relevant to the feasibility of collecting children's care outcome data into our interviews with 10-15 social service professionals, as planned under **IPE Q1**. These conversations will focus on current data collection practices, challenges faced, and potential areas for improvement regarding the tracking and reporting of outcomes such

as re-referrals for child abuse and neglect, transitions in child protection status, and the time on child protection plan. By tailoring these interviews to include specific questions on data management and reporting, we will gain insights into the practical aspects of data collection, which will help inform the design and implementation of robust data tracking mechanisms for the definitive trial.

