Our team have received training in diversity, equity, inclusion, and cultural competence. We are experienced in working with marginalised communities and therefore committed to conducting an inclusive and equitable evaluation. [name] is experienced in conducting research with ethnic minority communities and has published widely in this area. [name] has received numerous trainings regarding cultural competence and conducts research (1) translating westernised research protocols to indigenous persons, and (2) examining the experiences of black and ethnic minority staff within the NHS. [name] successfully worked with vulnerable and diverse families as a registered social worker for over 14 years applying relationship-based and inclusive practices. [name] and [name] have many years of experience of conducting research with marginalised and hard to reach populations who have often been excluded from previous research evaluations.

Through integrating these elements and the practical strategies, the evaluation will adhere to EDI principles and ensure the findings are representative and inclusive.

Ethics and registration

The study will be conducted in accordance with the principles of Good Clinical Practice, the Declaration of Helsinki and Caldicott principles. Participants will only be recruited to the study once independent full ethical approval has been granted by the University of Kent Social Research Ethics Committee and the trial will be registered in a recognised trial registry. Trial methods and data collection instruments will be assessed by our Advisory Board and their recommendations for changes will be incorporated.

We will ensure participants do not feel coerced to participate in the study. Once a participant is referred to the service any consent or assent to participate in the trial is theirs solely to make. Not consenting to the research will not impact on the BAU they receive, and this will be explained verbally and in writing. If a participant does consent it will be made clear that they can withdraw consent at any time during data collection for the study. Participants will be able to withdraw from any interventions and still provide follow-up data; withdraw, and have data already completed included in the trial analysis but provide no further additional data; or withdraw completely and have data already collected removed from the analysis.

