We will minimise the potential for participants and staff to experience any adverse or iatrogenic events. In our experience of conducting similar studies in similar populations the risk of adverse events is low, as is the risk of iatrogenic events. We will implement a standard operating procedure for the reporting of adverse events that involves an independent experienced third-party making recommendations on the severity of any event and whether they are associated with the trial. We will comply with the YEF safeguarding reporting criteria and provide details of any serious offences committed by participants. Staff involved in the study will have enhanced DBS accreditation and will be familiarised with safeguarding practice and procedures.

Data protection

All systems and personnel are approved for the management of clinical and sensitive data and are ISO certified to ISO27001 standard. This includes all physical systems, systems to detect intrusion, encryption of data from point of collection to storage, quality assurance and audit trails associated with any data collected. All identifiable data collected will be done with explicit consent and limited to data to allow participants to be contacted for follow-up. Data linkage will employ a unique identifier where the link to identifiable information will be stored on an encrypted secure database. Researchers will be trained to General Clinical Practice (GCP) standard and will comply with all relevant data protection legislation. Once final followup is completed, personally identifiable information will be deleted from the dataset held by the university and where consent has been granted for the study encrypted data will be transferred to the Youth Endowment Fund data archive. Data collection and management will be governed by a trial specific Standard Operating Procedure agreed and approved by ethics.

The basis of processing data is the public task basis to use their personal information. Where the Party is a public body, entity or authority, the applicable lawful basis for the processing of Personal Data under this ISA is provided for in the UK General Data Protection Regulation ("UK GDPR"), article 6 (Lawfulness of Processing), specifically article 6.1 (a) and (e) as well as article 9 (Processing of Special Categories of Personal Data), specifically article 9.2 (a), (h), (i) and (j).

Article 6.1

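### A family that formally withdraws cannot choose to stop questionnaires and contact while allowing data held by others to be collected to month 9

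*Protocol*

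**What the plan says.** Protocol, Ethics and registration, lists three levels of withdrawal:

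1. "Participants will be able to withdraw from any interventions and still provide follow-up data";
2. "withdraw, and have data already completed included in the trial analysis but provide no further additional data";
3. "or withdraw completely and have data already collected removed from the analysis".

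Several planned data items do not obviously come from the family:

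- **Social care outcomes.** Outcome measures, Parent-related outcomes, plans to collect "any further referrals, children's social care interventions or out of home placements over the nine months from baseline to follow-up". Table 2 lists social service involvement at baseline and nine months. Neither place names a source.
- **SDQ from others.** The Table 2 footnote foresees parent, practitioner and school versions. RQ4 compares parent and school reports for children under 11.
- **Case summaries.** Process measures and RQ10 take the interventions delivered, and adherence to them, from weekly summaries written by MST-CAN staff. Adherence is a progression criterion in Table 1.

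RQ5 is "To report on the feasibility of collecting children's social care outcome data". The Data protection section adds: "Data linkage will employ a unique identifier where the link to identifiable information will be stored on an encrypted secure database". It names no dataset, and it says that identifiable data are collected with explicit consent.

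**The concern.** A family may be content for the trial to use what the local authority, the school or the MST-CAN team already records, yet want no more questionnaires or calls. None of the three levels fits that wish. Level 1 concerns the intervention and keeps the family in follow-up. Levels 2 and 3 stop further data, and level 3 also removes what is already held.

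The families who formally withdraw may be those whose case has gone badly, with a new referral or a placement. If so, the social care outcomes would be missing for the families in whom they matter most. The loss could also differ by arm. Participants know their allocation, and a business-as-usual family has no trial intervention to leave, so level 1 offers it no relief from research burden. A definitive trial that copied the wording would inherit the same avoidable gap.

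**Working it through.** **1. The plan's own figure.** Sample size: 72 recruited, "with the expectation that we will successfully follow-up 58 at month 9". The upper follow-up threshold in Table 1 is 80%, and 0.80 × 72 = 57.6, which rounds to 58. The figure is reproduced. Expected without month-9 follow-up: 72 − 58 = 14, and 14/72 = 19.4%. This counts every reason for loss. The protocol gives no rate of formal withdrawal.

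**2. Each withdrawal level against each data source.**

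| Data to month 9 | Level 1 | Level 2 | Level 3 |
|---|---|---|---|
| Parent and child questionnaires | continue | stop | stop, earlier data removed |
| Social care outcomes | continue | stop or unclear | stop, earlier data removed |
| School SDQ | continue | stop or unclear | stop, earlier data removed |
| MST-CAN case summaries | continue while treated | stop or unclear | stop, earlier data removed |

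No column shows questionnaires stopping and the other rows continuing. That is the gap.

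**3. How far a descriptive proportion could move.** Let m be the share of families in an arm whose outcome is lost, p_r the event rate in retained families and p_w the rate in withdrawn families. The rate in all families is (1 − m)p_r + m·p_w, and the observed rate is p_r. The understatement is m(p_w − p_r), which cannot exceed m in either direction. With the same m in both arms, the arm difference cannot move by more than 2m.

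| Assumed m | Families of 72 | Limit, one arm | Limit, arm difference |
|---|---|---|---|
| 3% | 2.2 | 3 points | 6 points |
| 5% | 3.6 | 5 points | 10 points |
| 10% | 7.2 | 10 points | 20 points |
| 19.4% | 14 | 19.4 points | 38.8 points |

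These are arithmetic limits, not estimates. The last row treats every expected loss as a formal withdrawal.

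**4. A purely hypothetical illustration.** Take p_r = 20% and p_w = 40% to 60%; neither rate is in the protocol. The understatement is 1 to 2 points at m = 5%, 2 to 4 at m = 10%, and 4 to 8 at m = 19.4%. For comparison, the 95% half-width for a 20% proportion in 36 families is 1.96 × √(0.2 × 0.8/36) = 13.1 points. On these rates the shift is smaller than the pilot's sampling error.

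**5. Adherence.** With 36 families in the MST-CAN arm, each family whose case summaries are lost is worth 1/36 = 2.8 points against the Table 1 thresholds of 80%, 60% and 50%.

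**The case against.** The case against is substantial, and most of it narrows the point.

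- **Who is bound.** The levels apply to people who withdraw consent. A reader might infer that any family that drops out of contact loses its social care outcomes. The protocol does not support that: a family that stops answering has not withdrawn, and nothing bars collecting its data.
- **What the wording covers.** Level 2 speaks of what the participant will provide, and records held by a local authority are arguably not provided by the family. On that reading the level is silent on these sources rather than closing them. The ambiguity remains, and the explicit-consent statement under Data protection would make a careful data holder stop.
- **The source is inferred.** The protocol never says that the social care outcomes come from records. It is the natural reading, because they are local authority decisions, but it is an inference.
- **RQ5.** A reader might infer that lost records undermine RQ5. Under Data analysis, RQ5 is answered by interviews with 10–15 professionals: "These conversations will focus on current data collection practices, challenges faced, and potential areas for improvement regarding the tracking and reporting of outcomes such" (the list that follows includes re-referrals and changes of protection status). No retrieval rate or threshold is set, so a few withdrawals do not harm it.
- **Inference.** RQ9 restricts inferential analysis to the month-9 SDQ externalising score. No between-arm test of placement or re-referral is described, so a claim that an arm effect would vanish concerns no planned estimate. Continued collection would not recover a self- or parent-completed SDQ. A school SDQ kept after a parent stops would also have no parent report to pair with at month 9 for RQ4.
- **Documents not shown.** The consent forms and the data-management procedure may already separate these sources. That cannot be judged here, but the protocol's own list would still need to agree with them.

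**Conclusion.** The point holds in a limited form. For families who formally withdraw, the protocol's list has no level that ends questionnaires and contact while permitting data from others, and its middle level either stops those data or leaves their status undefined. The number affected is unknown. On the plan's own expectation it lies somewhere up to 14 of 72 families (19.4%), and that ceiling includes losses that are not withdrawals.

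What is exposed is the description of social care outcomes by arm, the adherence data behind a progression criterion, and any school SDQ that would otherwise arrive. The RQ9 analysis of self- or parent-completed SDQ and the RQ5 interviews are not affected.

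A reader might go further and conclude that the social care outcomes will be missing not at random, or lost unequally by arm. Both are plausible, but the document has no withdrawal rate, event rate or split by arm that would show either. The conclusion assumes that the social care outcomes are held by the local authority, which the protocol implies but does not state.

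This is a gap in a stated procedure that is cheap to close and worth closing in a pilot. It does not threaten the pilot's main conclusions.

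**What to change.** 1. In Outcome measures and Table 2, name the source of the social care outcomes: local authority records, family report or both.
2. In Ethics and registration, split the second withdrawal level into two:
   - (a) questionnaires and research contact stop, but the family agrees that social care records, the school SDQ and MST-CAN case summaries may still be collected to month 9;
   - (b) no further data of any kind from any source.
3. Take the choice under the consent arrangements in inclusion criterion 4: the parent decides for themselves and for children under 16, and those aged 16 or over decide for themselves. Use the same wording on the consent and withdrawal forms, subject to ethics approval.
4. Report the numbers at (a) and (b) by arm, separately from complete withdrawal and from loss of contact.

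Complete withdrawal stays available, so no family loses a choice. The sample size does not change. The cost is slightly longer forms, a slightly longer withdrawal conversation and an ethics wording change. The wording must rest on explicit agreement, because level (a) continues to collect sensitive data on children after research contact ends.
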